1.1 Synopsis

Protocol Title:

A randomized, open-label, multicenter, Phase 2b study to evaluate physical function, including balance and daily activity, in participants with castration-resistant prostate cancer treated with darolutamide or enzalutamide

Short Title:

DaroAcT: darolutamide physical function and daily activity study

Rationale:

There are multiple androgen receptor (AR) inhibitors indicated for prostate cancer with proven efficacy. However, these drugs are associated with adverse events including fatigue, cognitive dysfunctions, anorexia, sarcopenia, muscle weakness, and falls. There is an unmet medical need to improve patients' daily function, quality of life, and safety with an AR inhibitor with a better safety profile. Enzalutamide is the most frequently used AR inhibitor indicated for the treatment of patients with castration-resistant prostate cancer (CRPC).

The Phase 3 ARAMIS study of AR inhibitor darolutamide resulted in statistically significant improvement in metastasis-free survival compared to placebo (40.4 months vs. 22.0 months in the placebo arm) with a p-value of <0.001 and hazard ratio of 0.41 (95%CI: [0.34;0.50]). Treatment with darolutamide also resulted in a positive trend in overall survival and a delay in time to pain progression ([Fizazi et al. 2019](#)). The study also showed that darolutamide is well-tolerated and has a differentiated safety profile from other AR inhibitors (enzalutamide and apalutamide). However, currently there has not been a study to assess physical functioning and daily activities in patients treated with darolutamide.

The primary aim of this study is to evaluate the effects of treatment with darolutamide or enzalutamide on physical function as demonstrated by changes in balance, mobility, and cognitive function in participants with CRPC.

Objectives and Endpoints:

Objectives	Endpoints
Primary	

The primary objective of this study is to compare the effects of treatment with darolutamide vs. enzalutamide on physical function as assessed by the Timed Up and Go (TUG) test in participants with castration-resistant prostate cancer.
	
Proportion of participants with a worsening in TUG time during the 24-week period from baseline. Worsening is defined as an increase of at least 1 second in TUG time from baseline. (The minimum clinically important difference [MCID] in TUG time is 1 second (Davies et al. 2016))

Secondary	

The secondary objectives of this study are to:
 
 • Compare the effects of treatment with darolutamide vs. enzalutamide on physical function, as assessed by the TUG test at 12 and 24 weeks, and by 52 weeks. • Compare the effects of treatment with darolutamide vs. enzalutamide on physical function as assessed by Short Physical Performance Battery (SPPB) test at 12 and 24 weeks, and by 24 and 52 weeks. • Assess the effects of treatment with darolutamide vs. enzalutamide on daily activity as assessed by accelerometry at 12 and 24 weeks, and by 24 and 52 weeks. • Compare the effects of treatment with darolutamide vs. enzalutamide on cognitive function as assessed by Hopkins Verbal Learning Test-Revised (HVLTR), Trail Making Test (TMT), Controlled Oral Word Association (COWA), and Functional Assessment of Cancer Therapy – Cognitive questionnaire (FACT-Cog) • Compare the effects of treatment with darolutamide vs. enzalutamide on fatigue as assessed by the Brief Fatigue Inventory (BFI) • Compare the effects of treatment with darolutamide vs. enzalutamide on depression as assessed by the Patient Health Questionnaire-9 (PHQ-9) • Evaluate safety, including adverse events (AEs) of interest, of participants treated with darolutamide vs. enzalutamide 
 • Evaluate the effect of treatment with darolutamide or enzalutamide on prostate-specific antigen (PSA), survival status, and exposure 	
Physical Function:
 
 • Proportion of participants with an increase of at least 1 second in TUG time at 12 and 24 weeks and during the 52 weeks from baseline. • Time to worsening (increase of at least 1 second) in TUG time • Proportion of participants with a worsening in SPPB total score at 12 and 24 weeks and during the 24 weeks and 52 weeks from baseline. Worsening is defined as a decline of at least 0.5 points in SPPB total score. 
Daily Activity:
 
 • Mean change from baseline in daily physical activity at 12 and 24 weeks, and during the 24 weeks and 52 weeks from baseline. • Mean change from baseline in accelerometer-assessed proportion of time spent in light to vigorous physical activity based on a threshold of >100 activity counts per minute at 12 and 24 weeks, and during the 24 weeks and 52 weeks from baseline. 
Cognitive Function:
 
 • Proportion of participants with a decline in cognitive function during the 24 weeks and 52 weeks from baseline, as assessed by HVLTR, TMT, and COWA. See Table 8–1 for the definition of decline for each test. • Proportion of participants with a decline using a selected domain of FACT-Cog. Decline is defined as a decrease of >10 points during the 24 weeks and 52 weeks from baseline. 
Fatigue:
 
 • Proportion of participants with a worsening of fatigue during the 24 weeks and 52 weeks from baseline. Worsening is defined as an increase of at least 1 point in worst level of fatigue from baseline by 24 weeks and 52 weeks (based on item 3 of the BFI). • Proportion of participants with an increase of at least 1 point in fatigue interference by 24 weeks and 52 weeks from baseline (based on items 4A-F of the BFI).

Objectives	Endpoints
	
Depression:
 
 • Proportion of participants with a worsening in scores in the PHQ-9 during the 24 weeks and 52 weeks from baseline. Worsening is defined as an increase of at least 1 point in worst level of depression from baseline by 24 weeks and 52 weeks. 
Safety
 
 • All treatment emergent AEs, SAEs, and AEs leading to study intervention discontinuation • AEs of interest, including falls, fractures, and hypothyroidism 
Exposure and other:
 
 • Time to deterioration of KPS defined as at least a 10 point decline from baseline • Treatment exposure of the study intervention including time on treatment • Dose reductions of study intervention • Time to PSA progression (as per Prostate Cancer Working Group [PCWG3] criteria) • Survival status

Overall Design:

This randomized, open-label, multicenter, Phase 2b study is designed to evaluate darolutamide therapy in participants with CRPC who have not previously been treated with apalutamide, darolutamide, or enzalutamide. CRPC patients with a history of treatment with abiraterone may be eligible if they have not progressed and discontinued treatment within 6 months before signing the ICF for this study.

The study consists of two phases, a lead-in phase and a randomized phase. In the lead-in phase, approximately 30 participants will be treated with darolutamide. Following the evaluation of the lead-in phase, approximately 120 additional participants will be randomized in a 1:1 ratio to receive either darolutamide (600 mg twice daily) or enzalutamide (160 mg once daily) in the randomized phase of the study. Randomization will be stratified by age (<75, ≥75 years).

The endpoints used in this study are novel in a way that decline in physical function will be evaluated using objective measures such as TUG, SPPB, and accelerometry, therefore, the lead-in phase has been added to be able to assess compliance and the variability of the endpoints and overall feasibility of the study execution. The randomized phase of the study will start only after the primary evaluation of the lead-in phase. Depending on the results of the lead-in phase, the primary endpoint of the study and/or sample size for the randomized phase may be changed.

The primary evaluation of the lead-in phase will occur when the last participant in the lead-in phase has been on the study for at least 24 weeks, unless the participant discontinued due to lost to follow-up, withdrawal, or death.

Disclosure Statement:

This is an open-label treatment study consisting of a lead-in phase with one arm to be followed by a randomized phase with two arms.

Number of Participants:

- Lead-in phase: approximately 30 participants (darolutamide)
- Randomized phase: approximately 120 participants (1:1 darolutamide or enzalutamide)

Intervention Groups and Duration:

The following treatment arms are defined for this study:

[figure not shown]
- Darolutamide 600 mg (2 tablets of 300 mg) twice daily with food, equal to a total daily dose of 1200 mg
- Enzalutamide 160 mg (four 40 mg capsules) administered orally once daily. Capsules are to be swallowed whole. Enzalutamide can be taken with or without food.

All participants must continue to receive androgen deprivation therapy (ADT) of the investigator's choice (luteinizing hormone-releasing hormone [LHRH] agonist/antagonists) as standard therapy or have had orchiectomy.

Data Monitoring Committee: No

1.2 Schema

Figure 1–1: Study Periods

CRPC = castration-resistant prostate cancer; N = number of participants; R = randomization
Randomization will be stratified by age (<75 vs ≥75 years).

Table 1–1 Schedule of Activities for the Lead-in Phase (darolutamide)												
Assessment	Screening	Intervention + Observation Period								End of treatment visit (30 days after last dose) ^m	Survival follow-up ^{l,n}	
		Week 1 Day 1 ⁱ	Week 4 ^j	Week 8	Week 12	Week 24	Week 38	Week 52	from Week 53: Active follow up every 3 months ^{k,l}			
Time window allowed	within 21 days prior to first dose		± 7 days	± 7 days	± 7 days	± 7 days	± 14 days	± 7 days	± 1 month	+ 1 month	± 1 month	
Treatment dispensing / accountability		X	←=====→									
AE review ^b		←=====→										
AEs of interest review, including fall ^c		←=====→										
Timed Up and Go assessment (TUG) ^d	X ^h	X ^h			X	X		X	X			
Short Physical Performance Battery (SPPB) ^d		X			X	X		X	X			
Accelerometry assessment ^e	X				X	X		X	X			
Cognitive function ^f		X				X		X	X			
Brief Fatigue Inventory (BFI) ^g		X	X	X	X	X		X				
Patient Health Questionnaire (PHQ-9)		X	X	X	X	X		X	X			
Survival status											X	

X = measure/action to be performed at the time point indicated

←=====→ = measure/action to be performed continually during the time period indicated

AE = adverse event; BFI = Brief Fatigue Inventory; COWA = Controlled Oral Word Association; CRF = case report form; HVLTR = Hopkins Verbal Learning Test - Revised; PHQ-9 = Patient health questionnaire-9; PSA = prostate-specific antigen; SPPB = Short Physical Performance Battery; TMT = Trail Making Test; TUG = Timed Up and Go

- a PSA will be assessed at the same time as other laboratory assessments. A time window of ± 14 days is allowed for laboratory and PSA assessments.
- b Including survival, pain, radiographic progression, metastases, and skeletal events
- c AEs of interest are fractures, falls, and hypothyroidism
- d Physical function tests include SPPB and the TUG assessment.
- e Accelerometry assessment will require the participant to wear an accelerometry device on the wrist or hip for a minimum of 7 days at each time point. The first accelerometry assessment is to be performed before the first dose (i.e. during screening).
- f Cognitive function tests include the HVLTR, TMT, and COWA, as well as the patient-reported outcome questionnaire FACT-Cog.
- g BFI is a 5 minute self-assessment tool that identifies fatigue in cancer participants over a 24-hour period.
- h The first TUG assessment is to be performed before the first dose (either during screening or Week 1 Day 1).
- i Once the baseline procedures are completed, the first administration of study intervention will be provided at the study center and the participant will be provided with additional medication to take as scheduled through the Week 4 visit. (Each participant will be instructed to bring any remaining drug back to the center at the Week 4 visit.)
- j At this and each subsequent visit, the participant will return dispensed but unused study intervention to the investigator for recording on the CRF. Reasons for non-compliance will be recorded. A new supply of study drug sufficient to meet the dosing requirements of each participant will be dispensed.
- k Participants remaining on treatment beyond Week 52 will continue, where possible, to receive study intervention and assessments until the final evaluation of the randomized phase (i.e. at Week 52 for the last participant, see Section 4.4.1).
- l Prior to the final evaluation of the randomized phase of the study, all participants will go into Week 53 active follow-up or survival follow-up as applicable.
- m Each participant should complete an end of treatment visit after discontinuation of study intervention for any reason. All anti-cancer treatments after discontinuation of study intervention in this study will be recorded on the CRF at the end of treatment visit. See Section 4.4.2 for more details once the date of the final evaluation of the randomized phase is determined.
- n Survival will be followed with contact with the participant and/or his caregiver every 3 months following the date of last treatment until the end of the study for participants treated with darolutamide (see Section 4.4.2).

Table 1–2 Schedule of Activities for the Randomized Phase (darolutamide, enzalutamide)													
Assessment	Screening	Randomization	Intervention + Observation Period									End of treatment visit (30 days after last dose) ⁿ	Survival follow-up ^{m,o}
			Week 1 Day 1 ⁱ	Week 4 ^k	Week 8	Week 12	Week 24	Week 38	Week 52	from Week 53: Active follow up every 3 months ^{l,m}			
Time window allowed	within 21 days prior to randomization		within 21 days after randomization	± 7 days	± 7 days	± 7 days	± 7 days	± 14 days	± 7 days	± 1 month	+ 1 month	± 1 month	
Treatment dispensing / accountability			X	←=====→									
AE review ^b			←=====→										
AEs of interest review, including fall ^c			←=====→										
Timed Up and Go assessment (TUG) ^d	X ^h		X ^h			X	X		X	X			
Short Physical Performance Battery (SPPB) ^d			X			X	X		X	X			
Accelerometry assessment ^e	X					X	X		X	X			
Cognitive function ^f			X				X		X	X			
Brief Fatigue Inventory (BFI) ^g			X	X	X	X	X		X				
Patient Health Questionnaire (PHQ-9)			X	X	X	X	X		X	X			
Survival status												X	

X = measure/action to be performed at the time point indicated

←=====→ = measure/action to be performed continually during the time period indicated

AE = adverse event; BFI = Brief Fatigue Inventory; COWA = Controlled Oral Word Association; CRF = case report form; HVLTR = Hopkins Verbal Learning Test - Revised; PHQ-9 = Patient health questionnaire-9; PSA = prostate-specific antigen; SPPB = Short Physical Performance Battery; TMT = Trail Making Test; TUG = Timed Up and Go

- a PSA will be assessed at the same time as other laboratory assessments. A time window of ± 14 days is allowed for laboratory and PSA assessments.
- b Including survival, pain, radiographic progression, metastases, and skeletal events
- c AEs of interest are fractures, falls, and hypothyroidism
- d Physical function tests include SPPB and the TUG assessment.
- e Accelerometry assessment will require the participant to wear an accelerometry device on the wrist or hip for a minimum of 7 days at each time point. The first accelerometry assessment is to be performed before the first dose (i.e. during screening).
- f Cognitive function tests include the HVLTR, TMT, and COWA, as well as the patient-reported outcome questionnaire FACT-Cog.
- g BFI is a 5 minute self-assessment tool that identifies fatigue in cancer participants over a 24-hour period.
- h The first TUG assessment is to be performed before the first dose (either during screening or Week 1 Day 1).
- i Once the baseline procedures are completed, the first administration of study intervention will be provided at the study center and the participant will be provided with additional medication to take as scheduled through the Week 4 visit. (Each participant will be instructed to bring any remaining drug back to the center at the Week 4 visit.)
- j Laboratory and PSA analyses and the physical examination will need to be repeated if they are not within 21 days from randomization. Week 1 Day 1 cannot be longer than 3 weeks from randomization.
- k At this and each subsequent visit, the participant will return dispensed but unused study intervention to the investigator for recording on the CRF. Reasons for non-compliance will be recorded. A new supply of study drug sufficient to meet the dosing requirements of each participant will be dispensed.
- l Participants remaining on treatment beyond Week 52 will continue, where possible, to receive study intervention and assessments until the final evaluation of the randomized phase (i.e. at Week 52 for the last participant, see Section 4.4.1).
- m Prior to the final evaluation of the randomized phase of the study, all participants will go into Week 53 active follow-up or survival follow-up as applicable.
- n Each participant should complete an end of treatment visit after discontinuation of study intervention for any reason. All anti-cancer treatments after discontinuation study intervention in this study will be recorded on the CRF at the end of treatment visit. See Section 4.4.2 for more details once the date of the final evaluation of the randomized phase is determined.
- o Survival will be followed with contact with the participant and/or his caregiver every 3 months following the date of last treatment until the end of the study for participants treated with darolutamide, and until the final evaluation of the randomized phase for participants treated with enzalutamide (see Section 4.4.2).

2. Introduction

Prostate cancer is the second most common cancer and the fifth leading cause of cancer death among men worldwide ([World Health Organization 2017](#)). It is the most common non-cutaneous cancer and the second leading cause of cancer-related deaths in men in Europe ([World Health Organization 2008](#)) and the United States (USA) ([Hirsch et al. 2001](#)). The most significant morbidity of prostate cancer is bone metastases.

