5.2 Exclusion Criteria

Participants are excluded from the study if any of the following criteria apply:

Medical Conditions

1. Symptomatic local-regional disease that requires medical intervention including moderate/severe urinary obstruction or hydronephrosis with abnormal renal function due to prostate cancer. Participants with visceral metastasis will be excluded.
2. Severe or uncontrolled concurrent disease, infection, or comorbidity
3. Past (within 6 months before the start of study intervention) or concurrent stroke, myocardial infarction, severe/unstable angina pectoris, coronary/peripheral artery bypass graft, and/or congestive heart failure (New York Heart Association Class III or IV)
4. Uncontrolled clinically significant hypertension
5. Prior malignancy. Adequately treated basal cell or squamous cell carcinoma of the skin or superficial bladder cancer that has not spread behind the connective tissue layer (i.e. pTis, pTa, and pT1) is allowed, as well as any other cancer for which treatment has been completed 3 years before the start of study intervention and from which the participant has been disease free
6. Known metastatic brain or meningeal tumors
7. Prior or concurrent central nervous system disease, such as epilepsy, Parkinson's disease, Alzheimer's disease, dementia, or multiple sclerosis
8. Active viral hepatitis, active human immunodeficiency virus (HIV), or chronic liver disease
9. Gastrointestinal disorder or procedure that is expected to interfere significantly with absorption of study treatment
10. Major surgical procedure or significant traumatic injury within 28 days before the start of study intervention

11. Seizure disorder requiring medication
12. Non-healing wound, ulcer, or bone fracture
13. Substance abuse, medical, psychological, or social conditions that may interfere with the participant's participation in the study or evaluation of the study results
14. Non-ambulatory participants who need a wheelchair. Other assistive devices (e.g., cane or walker) are permitted.
15. Any illness or medical condition that is unstable or could jeopardize the safety of the participant and his compliance in the study
16. Clinically significant limitations in cognitive function and/or physical function, such as >20 seconds in the TUG assessment

Prior/Concomitant Therapy

17. Prior treatment with any of the following:
 - Second-generation AR inhibitors, such as enzalutamide, apalutamide, or darolutamide

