6.3 Measures to Minimize Bias: Randomization

This is an open-label study; however, all participants in the randomized phase will be centrally assigned to randomized study intervention using an Interactive Web Response System (IWRS). Before the study is initiated, the log in information & directions for the IWRS will be provided to each site.

The site will contact the IWRS prior to the start of study intervention administration for each participant. The site will record the intervention assignment in the participant's source documents and on the applicable case report form, if required. Potential bias will be reduced by central randomization.

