7.3 Lost to Follow up

A participant will be considered lost to follow-up if he repeatedly fails to return for scheduled visits and is unable to be contacted by the study site.

The following actions must be taken if a participant fails to return to the clinic for a required study visit:

- The site must attempt to contact the participant and reschedule the missed visit as soon as possible and counsel the participant on the importance of maintaining the assigned visit schedule and ascertain whether or not the participant wishes to and/or should continue in the study.
- Before a participant is deemed lost to follow up, the investigator or designee must make every effort to regain contact with the participant (where possible, 3 telephone calls and, if necessary, a certified letter to the participant's last known mailing address or local equivalent methods). These contact attempts should be documented in the participant's medical record.
- Should the participant continue to be unreachable, he/she will be considered lost to follow-up.

Discontinuation of specific sites or of the study as a whole are handled as part of Appendix 1 (Section 10.1).

8. Study Assessments and Procedures

- Study procedures and their timing are summarized in the SoA (Section 1.3). Protocol waivers or exemptions are not allowed.
- Immediate safety concerns should be discussed with the sponsor immediately upon occurrence or awareness to determine if the participant should continue or discontinue study intervention.
- Adherence to the study design requirements, including those specified in the SoA (Section 1.3), is essential and required for study conduct.
- All screening evaluations must be completed and reviewed to confirm that potential participants meet all eligibility criteria. The investigator will maintain a screening log to record details of all participants screened and to confirm eligibility or record reasons for screening failure, as applicable.

- Procedures conducted as part of the participant's routine clinical management (e.g., blood count) and obtained before signing of the ICF may be utilized for screening or baseline purposes provided the procedures met the protocol-specified criteria and were performed within the time frame defined in the SoA (Section 1.3).

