9.4.2 Safety Analyses

All safety analyses will be performed on the Safety population.

Endpoints measuring physical function, cognitive function, and daily activity will also be performed on the Safety population.

Endpoint	Statistical Analysis Methods
Primary	
The primary variable in this study is the proportion of participants with a worsening in TUG time during the 24-week period from baseline. Worsening is defined as an increase of at least 1 second in TUG time from baseline by 24 weeks.
 
 At each assessment, change in TUG test time (seconds) from baseline will be calculated, and the status will be categorized as: improved, stable, or declined using the MCID of 1 second. Decline in physical function is defined as at least a 1-second increase from baseline in TUG time in each arm by 24 weeks. The proportion of participants with a decline and the 95% CIs will be summarized for each treatment arm. This rate will be compared between the two arms using Cochran-Mantel-Haenszel test adjusting for stratification factors as captured by IWRS.

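### In the randomised phase the first TUG may be done after open-label allocation, although a TUG above 20 seconds is named as an example of an excluding limitation

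*Protocol*

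**What the plan says.** **Eligibility.** Protocol 5.2, criterion 16, excludes men with "Clinically significant limitations in cognitive function and/or physical function, such as >20 seconds in the TUG assessment". Protocol section 8 adds: "All screening evaluations must be completed and reviewed to confirm that potential participants meet all eligibility criteria". The schedule in SAP Table 8-2 marks the inclusion and exclusion check in the Screening column only. The opening of Protocol section 5 rules out waivers of enrolment criteria, and section 8 repeats that waivers are not allowed.

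**Timing of the TUG.** Protocol Table 1-2 marks a TUG at Screening and at Week 1 Day 1. Both marks carry footnote h: "The first TUG assessment is to be performed before the first dose (either during screening or Week 1 Day 1". SAP Table 8-2 has the same footnote.

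**Timing of randomisation.** In Table 1-2 screening is "within 21 days prior to randomization" and Week 1 Day 1 is "within 21 days after randomization". Footnote j repeats the limit: "Week 1 Day 1 cannot be longer than 3 weeks from randomization".

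**Blinding.** Protocol 6.3 states: "This is an open-label study; however, all participants in the randomized phase will be centrally assigned to randomized study intervention". Table 8-1 asks for independent blinded TUG assessors only where that can be arranged.

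**Analysis set.** Protocol 9.4.2 states: "Endpoints measuring physical function, cognitive function, and daily activity will also be performed on the Safety population". Under Protocol 9.3 and SAP Table 3 that population contains only men who took some study treatment, whether or not they were eligible. Each instrument further needs a baseline and at least one later assessment.

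**The concern.** An eligibility test should be complete before allocation. Here the only numeric threshold in criterion 16 comes from a test that may first be done after the arm has been assigned and disclosed. The lead-in table has an identically worded footnote, but no randomisation takes place there, so the problem is confined to the randomised phase.

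The stake is the primary comparison. A man randomised and then not dosed because of a slow Day 1 TUG is absent from the Safety population. The SAP's sensitivity analysis, which counts missing TUG times as worsening (SAP 4.2 and 5.5.1), does not bring him back, because he is outside the set to which it applies. If the limit were enforced in the same way in both arms, the cost would be some precision. If it were enforced differently with the arm known, the comparison would be biased, and it would be biased through men with the slowest walking times.

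**Working it through.** **1. Order of events that the text allows**

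| Step | Earliest and latest | Source |
|---|---|---|
| Screening, TUG optional under footnote h | 21 to 0 days before randomisation | Protocol Table 1-2 |
| Randomisation, arm disclosed | day 0 | Protocol 6.3 |
| Week 1 Day 1, first TUG allowed before dosing | 0 to 21 days after randomisation | Table 1-2, footnotes h and j |

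The general rule in section 8 requires screening evaluations to be completed and reviewed, but it does not say that the TUG must be one of them. Footnote h makes the screening TUG optional. By contrast, footnote e of the same table ties the first accelerometry assessment to screening. The passages therefore conflict, and none overrides the others.

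**2. What follows from a first Day 1 TUG above 20 seconds**

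- Not dosed, as the ban on waivers implies: he is in the FAS and the disposition tables, but not in the Safety population or the primary analysis.
- Dosed despite the criterion: this is a protocol deviation, and he remains in the Safety population.
- No section says how this case is to be handled.

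**3. The plan's sample size, reproduced**

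Inputs from Protocol 9.2: 20% against 40% worsening, one-sided alpha 10%, power 85%, drop-out 10%, about 120 men randomised 1:1.

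- n per arm = (1.2816 + 1.0364)² × (0.20×0.80 + 0.40×0.60) / 0.20² = 53.7, so 54.
- 108 / 0.90 = 120, which matches the plan.
- Power at 54 per arm is 85.1% with unpooled variance and 84.4% with pooled variance under the null. Step 5 uses the pooled form.

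**4. Illustration: removal from one arm only**

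The number removed (k) and their 60% risk are assumptions; neither is in the documents.

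Darolutamide rate = (0.20×54 − 0.60k) / (54 − k)

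- k = 3: (10.8 − 1.8) / 51 = 17.6%, a shift of 2.4 points.
- k = 4: (10.8 − 2.4) / 50 = 16.8%, a shift of 3.2 points.

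The direction depends on the arm. With k = 3 removed from enzalutamide only, (0.40×54 − 1.8) / 51 = 19.8 / 51 = 38.8%, a shift of 1.2 points against darolutamide.

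For false positives, assume no true difference, 30% worsening in both arms, removal from the darolutamide arm only, and removed men worsening at 50% to 70%. The remaining darolutamide rate is (0.30 − fq)/(1 − f), where f is the fraction removed and q is their risk. With f = 5% it is 28.9% to 27.9%.

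| Removed from darolutamide arm | One-sided type I error (nominal 10%) |
|---|---|
| 2% | 10.8% to 11.7% |
| 5% | 12.2% to 14.8% |
| 10% | 15.0% to 21.7% |

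**5. Illustration: even loss**

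Six men (5% of 120), three per arm, leave 51 evaluable per arm if they come on top of the planned drop-out. Pooled power = Φ[(0.20 − 1.2816×√(2×0.30×0.70/51)) / √(0.40/51)] = 82.8%, against 84.4% at 54.

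**The case against.** The strongest reply is that the documents already intend eligibility to be settled at screening. A TUG is marked in that column, SAP Table 8-2 puts the criteria check there, section 8 requires review, and footnote h does not mention eligibility. A site reading all of this together would test before randomising. That stands as evidence of intent, and many sites may do so. It does not remove the option that footnote h gives in plain terms.

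Four stronger readings are tempting, and the documents do not support them:

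- *The site may choose, knowing the arm, whether to dose an ineligible man.* Waivers are ruled out in sections 5 and 8, so the protocol sanctions no such choice. Selective enforcement would be a deviation, which SAP 5.3.3 provides for classifying. The risk lies in uneven practice.
- *Criterion 16 rests on the TUG.* The 20-second limit is an example within a wider judgement on cognitive or physical limitation. KPS of at least 80, the wheelchair exclusion (criterion 14), criterion 26 on ability to complete the tests, and the screening physical examination should also find many very slow men before randomisation.
- *The treatment effect will be inflated by 2 to 3 points.* The documents give no frequency of TUG above 20 seconds and no risk of worsening for such men. The figures need several such men, all untested at screening and all removed from one arm. Undosed men could also fall within the 10% drop-out allowance.
- *The footnote was carried over by mistake from the lead-in table.* The documents show identical wording, not how it came about.

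It is also fair to say that the randomised design is provisional until the lead-in has been reviewed (Protocol 4.1, SAP 3.1). That makes the correction easy to time; it does not make it unnecessary.

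**Conclusion.** The point holds as a conflict between passages with a possible route to bias. Footnote h allows the first TUG up to 21 days after open-label randomisation, while criterion 16 and section 8 call for it to be known before. A man found over the limit at that stage would, under the ban on waivers, go undosed and leave the primary analysis.

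The size cannot be established from the documents. The 2.4-point shift, set against a planned difference of 20 points, and the type I error range show only what uneven removal could do under the stated assumptions. If losses are even, the cost is small: about 1.6 points of power for six men (84.4% − 82.8%). The stated sample size is unaffected. The case for acting is that the correction is almost free.

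**What to change.** In Protocol Table 1-2 and SAP Table 8-2, reconcile footnote h with criterion 16 and section 8. State, for the randomised phase only, that the TUG used for criterion 16 is performed and reviewed during screening, before IWRS randomisation. The lead-in tables can stay as they are. A Day 1 pre-dose TUG may still be taken and would serve as baseline under SAP 5.1.1, which uses the last value before first exposure.

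This change does not cover everything. Screening and Day 1 can be up to 42 days apart (21 + 21), so a man who passes at screening could still exceed 20 seconds on Day 1. The sponsor should reconcile criterion 16, the ban on waivers and the Safety population definition so that the handling and analysis of such a man are stated in advance and are the same in both arms. This review does not propose what that handling should be.

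The cost is one footnote in each document plus a sentence on handling, and the end of the lead-in review is a natural time to make the change. The downside is that the screening TUG, already in the schedule, is no longer optional.
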